- For patients that decline re-enrollment for full safety and effectiveness data collection or who have discontinued from the Registry for other reasons, physicians will be asked to obtain the patient's consent to data release for the completion of a simplified Healthcare Provider (HCP) questionnaire on an annual basis. The first data collection period will capture data from the time of patient's discontinuation of the Registry through the start of the direct to HCP process. The questionnaire focuses on the collection of surgeries or hospitalizations and adverse events of special interest and Crohn's related medication use since registry discontinuation. The questionnaire may be completed by the registry physician or the patient's current HCP (if they are no longer under the care of a registry physician). An HCP is not considered a participating investigator in the registry since they are only completing an annual questionnaire on behalf of a former registry patient. Participating registry investigators for which all of their patients have discontinued from registry participation may convert to an HCP status if their patients(s) choose to participate in the HCP process.

If treatment with Humira is permanently discontinued for any reason, patients will be encouraged to remain in the registry or to participate in the direct to HCP process unless consent is withdrawn.

When applicable, information about the effectiveness of Humira therapy will be provided by the patients and their physician. Effectiveness of therapy provided by the patient will be collected with PROs beginning with the registry enrollment visit, at regularly scheduled visits which are closest to Months 3, 6, 9, 12, and every 6 months thereafter, if part of routine clinical assessment. The following PROs will be used: Short Inflammatory Bowel Disease Questionnaire (SIBDQ), Health Care Resource Utilization (Unscheduled Outpatient Visits, Emergency Room Visits and Hospitalizations Questionnaire), and Work Productivity and Activity Impairment (WPAI). There are approximately 20 questions in the PRO assessments and it is expected that it will take approximately 15 minutes to complete them. Effectiveness of therapy will be collected through the Physician's Global Assessment beginning with the Registry enrollment visit and at regularly scheduled visits which are closest to Months 3, 6, 9, 12, and every

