6 months thereafter, if part of routine clinical assessment. Effectiveness measures will only be collected for patients receiving Humira.

Serious adverse events (SAE) and adverse events of interest will be recorded throughout the patient's participation in the registry or direct to HCP process and/or until 70 days following discontinuation of Humira/UMIRA administration have elapsed (which ever period is longer).

Adverse events of interest for this Registry include:

- Serious opportunistic infections, e.g., invasive fungal infections and TB
- Lymphoma including hepatosplenic T-cell lymphoma; leukemia, non-melanoma skin cancer (NMSC)
- Other malignancies (excluding lymphoma, leukemia and NMSC which are recorded separately)
- Immune reactions including lupus, lupus-like reactions and serious allergic reactions
- Congestive heart failure (CHF)
- Cerebrovascular accident (CVA)
- Myocardial infarction (MI)
- CNS demyelinating disorders (including Multiple Sclerosis and Guillain-Barré syndrome)
- Hepatic events that are serious or lead to permanent discontinuation of Humira (e.g., persistent liver function test abnormalities, acute liver failure and other serious hepatic events)
- Hematologic events that are serious or lead to permanent discontinuation of Humira (e.g., Aplastic anemia, Granulocytopenia, Granulocytes maturation Arrest, Leucopenia, Neutropenia, Pancytopenia and Thrombocytopenia)
- Worsening or new onset of Psoriasis
- Vasculitis

- Diverticulitis
- Intestinal perforation
- Occurrence of symptomatic intestinal obstruction
- Events leading to premature discontinuation of HUMIRA

Information on all concomitant medications will be captured at the time of enrollment into the Registry. Information on medications taken for CD (including dose changes) and a complete list of all medications taken at the time of a serious adverse events or adverse events of interest will be collected throughout the Registry.

This is a global registry being conducted in the US, Europe, Canada, South Africa, New Zealand and Australia and as such there are multiple local product labels. In Europe, Humira is registered for patients with severe Crohn's disease, while in the other regions it is registered for patients with moderate to severe disease. This protocol has been designed to accommodate all product labels.

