6.3.2 Effectiveness Variables

Information to evaluate the effectiveness of adalimumab therapy will be collected from patients and their physicians if part of routine clinical assessment. In the event adalimumab therapy is interrupted, effectiveness variables will be collected during the interruption.

The effectiveness of therapy evaluation provided by the subject will be collected with PROs beginning with the study enrollment visit, at regularly scheduled visits which are closest to Months 3, 6, 9, 12, and every 6 months thereafter, if part of routine clinical assessment. The following PROs will be used:

- SIBDQ,
- Health Care Resource Utilization (Unscheduled Outpatient Visits, Emergency Room Visits and Hospitalizations Questionnaire),
- WPAI.

There are approximately 20 questions in the PRO assessments and it is expected that it will take approximately 15 minutes to complete them.

Effectiveness of therapy provided by the study physician will be collected through the Physician's Global Assessment, if part of routine clinical assessment. The following assessments will be collected:

- General Well Being,

- Abdominal Pain,
- Diarrhea,
- Blood in Stool,
- Abdominal Mass,
- Crohn's Disease Related Complications.

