10.0 Statistical Methods and Determination of Sample Size

10.1 Statistical and Analytical Plans

Analyzable Populations:

Safety Populations During the Registry:

The Registry Safety Population consists of all patients who received at least one dose of Humira (adalimumab) in the Registry. This will be the population for safety analyses in the Registry and include safety data collected during the Registry only.

The "Episodic Dosing" Population will consist of patients in the Registry Safety Population who:

- discontinue Humira (adalimumab) at least once for more than 70 days and receive at least one dose of adalimumab after the treatment interruption,
- do not receive any other biologics during the treatment interruption and,
- provide data before and after Humira (adalimumab) treatment interruption period(s)
- and include safety data collected during the Registry only.

For patients previously treated with commercial Humira before enrollment into the Registry, Day 1 of adalimumab treatment will be the 1st day of Humira therapy, i.e., before enrollment into the Registry. Detailed information on concomitant medications, safety and effectiveness between the 1st dose of Humir and enrollment into the Registry will be available for these patients.

Re-enrollment Safety Population:

The Re-enrollment Safety Population consists of all patients who were discontinued from the Registry due to prior protocol withdrawal criteria (i.e., patients who have discontinued Humira therapy) or discontinued for other reasons and re-consent to participation in the Registry. This will be the population for safety analyses of data collected during the re-enrollment period.

For patients that re-enroll in the Registry, safety information collected between registry discontinuation and re-enrollment based on a retrospective review of their patient records will be analyzed separately.

HCP Safety Population:

The HCP Safety Population consists of all patients that decline re-enrollment to participation in the Registry or who have discontinued from the Registry for other reasons and consent to data release for the completion of a simplified HCP questionnaire in the direct to HCP process. This will be the population for safety analyses of data collected on HCP questionnaire.

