10.4 Effectiveness Analyses

Effectiveness parameters measured over the course of registry, include change from registry enrollment in the following measures: SIBDQ, Health Care Resource Utilization, WPAI, and Physician's Global Assessment.

The Physician's Global Assessment and SIBDQ scores will be summarized descriptively at each Registry visit. Additionally, changes from Registry enrollment by Registry visit will also be summarized for these outcomes using descriptive statistics. Health Resource Utilization and WPAI will also be summarized with descriptive statistics at each Registry visit.

For efficacy analyses of the "episodic dosing" population, only patients providing evaluations of efficacy at the two timepoints described below will be considered:

- data prior to the interruption in dosing, specifically at/after 12 weeks from enrollment in the Registry study.
- data after the dosing interruption is over, specifically, at/after 12 weeks upon resumption of Humira. For these patients, efficacy data at/after 12 weeks of

the 1st treatment in the Registry and at/after 12 weeks after the restart of Humira treatment during the Registry study will be summarized.

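### The effectiveness analysis of restarting Humira leaves out patients who permanently stop again before an evaluation at least 12 weeks after restart, so its post-restart results probably look better than those of all who restarted

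*Protocol*

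**What the plan says.** Protocol Section 10.1 places a patient in the Episodic Dosing Population if, among other conditions, they "discontinue Humira (adalimumab) at least once for more than 70 days and receive at least one dose of adalimumab after the treatment interruption". The patient must also take no other biologic during the gap and have data from both before and after it. No minimum time on re-treatment is set.

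Section 10.4 then narrows the effectiveness analysis of this population: "only patients providing evaluations of efficacy at the two timepoints described below will be considered". The first timepoint is "data prior to the interruption in dosing, specifically at/after 12 weeks from enrollment in the Registry study". The second is "data after the dosing interruption is over, specifically, at/after 12 weeks upon resumption of Humira". Only these data are summarised. The section provides no count, category or other handling for restarters who lack the second evaluation.

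Two sections govern whether that evaluation can exist for someone who stops again:

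- Section 6.0: "Effectiveness measures will only be collected for patients receiving Humira".
- Section 6.3.2: "In the event adalimumab therapy is interrupted, effectiveness variables will be collected during the interruption".

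These conflict for interruptions. For permanent stops only Section 6.0 speaks, and it ends collection. Patient-reported outcomes are collected "at regularly scheduled visits which are closest to Months 3, 6, 9, 12, and every 6 months thereafter", where this is part of routine assessment, and Section 6.0 gives the Physician's Global Assessment the same timing.

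**The concern.** The rule decides who is analysed by something that happens after restart, namely still supplying an evaluation 12 weeks or more later. Stopping again early for lack of effect or an adverse reaction is itself an outcome of re-treatment, and the rule removes those patients instead of reporting them. The before-and-after summary could then look stable even if a fair number of restarts ended early.

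No other effectiveness analysis in the protocol addresses dose interruption, so nothing else corrects the picture. This is also not a detail left open for a statistical analysis plan: the protocol states the exclusion, and a plan that follows it inherits the selection.

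**Working it through.** **Who can enter the analysis.** Setting Sections 10.1, 10.4 and 6.0 side by side, for patients in the Episodic Dosing Population who have the pre-interruption evaluation:

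| Course after restart | Evaluation at or after 12 weeks? | In the 10.4 analysis? |
|---|---|---|
| Stays on Humira, good response | Yes, if assessed | Yes |
| Stays on Humira, poor response | Yes, if assessed | Yes |
| Permanently stops before the qualifying visit | No (Section 6.0) | No |
| Pauses again before the visit | Depends on 6.0 or 6.3.2 | Unclear |
| Follow-up ends, or not assessed in routine care | No | No |

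The third row is the problem. The last row is also lost, but without a clear direction.

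**When the qualifying visit falls.** After Month 12, visits are 6 months (26 weeks) apart. If visits are exactly on schedule, the first one at or after 12 weeks from restart falls between 12 and 12 + 26 = 38 weeks; if restarts are spread evenly between visits, the mean is (12 + 38)/2 = 25 weeks. With 3-monthly spacing (13 weeks), which applies only up to Month 12, the range is 12 to 25 weeks.

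**A reference rate.** The protocol gives no rate of early re-treatment failure and no figure for this analysis. Its only dropout figure is in Section 10.7: a median of 3 years in two long-term trials. That figure reproduces:

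- λ = ln 2 / 3 = 0.231 per year.
- Person-time over 6 years = (1 − e^(−0.231×6))/0.231 = 3.246 years per patient, and 5,000 × 3.246 = 16,230 patient-years, as stated.

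Applied to restarters, as a reference only:

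- Lost by 12 weeks: 1 − e^(−0.231×12/52) = 1 − 0.948 = 5.2%.
- Lost by 38 weeks: 1 − e^(−0.231×38/52) = 1 − 0.845 = 15.5%.
- Mean loss with the visit uniform on 12 to 38 weeks: 1 − (0.9481 − 0.8447)/(0.231×26/52) = 1 − 0.1034/0.1155 = 10.5%.

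**What a given loss does to a mean score.** Let f be the share of restarters left out, m_E the mean among those evaluated and m_L the mean that those left out would have had. The mean over all restarters is (1 − f)·m_E + f·m_L, so the restricted summary differs from it by f·(m_E − m_L). At f = 5.2% or 10.5%, the difference is about 5% or 10% of the gap between the groups. At an assumed f of 30%, it is 30% of that gap. The protocol fixes neither f nor m_L, so the bias itself cannot be computed.

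**The case against.** **Limited stakes.** This is a descriptive summary under the secondary objective (Sections 5.0 and 10.2), with no test and no stated claim that benefit returns. The restriction is disclosed, a similar 12-week condition applies before the interruption, and Section 10.2 reports the number of observations. All of this stands and limits the weight of the point. But the number evaluated does not show how many restarted, and a condition on the earlier value does not bring back early re-treatment failures.

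**Failed restarts appear elsewhere.** Events leading to premature discontinuation and serious allergic reactions are adverse events of interest (Section 7.1.2). Section 10.5 summarises such events before and after the interruption, with no 12-week condition. So a reader who inferred that failed restarts vanish from the registry would be wrong. Those tables do not, however, put the patients back into the effectiveness summary.

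**Section 6.3.2.** If it governs, patients who only pause again may still qualify, because Section 10.4 does not require them to be on drug at the second evaluation. This narrows the loss for pauses but leaves permanent stops untouched.

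**Selection on benefit.** A reader might infer that a patient must tolerate and benefit from Humira to be counted. The documents do not support this: no response is required, and a poor responder who remains on treatment is included with a poor score.

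**A responder correction.** A reader might also convert the loss into a corrected success share, for example 70% × (1 − 0.105) = 63%. The protocol defines no endpoint of regained status, the 70% would be invented, and the sum counts every loss as a failure, including end of follow-up and missing routine assessment. No planned output corresponds to it.

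**Timing.** The 12-to-38-week wait assumes exact visits after Month 12. Section 6.4.8 accepts the visit closest to schedule, so real waits will vary.

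**Conclusion.** The point holds in a limited form. Section 10.4, read with Section 6.0, leaves restarters who permanently stop before the qualifying evaluation out of the only effectiveness analysis of interruption. Its post-restart results describe patients who stayed on treatment and were evaluated. They probably look better than they would for all who restarted.

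That direction rests on one assumption: early stoppers do worse, on average, than those evaluated. The size is unknown. About 5% lost by 12 weeks, or about 10% by a visit 12 to 38 weeks after restart, is a reference from general trial attrition and not an estimate of re-treatment failure, which could be higher or lower. The primary safety objective is unaffected. The change is worth making because the rule is explicit, its likely direction favours the drug, and the data needed for better reporting are already collected.

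**What to change.** In Section 10.4:

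- Take as denominator all Episodic Dosing Population patients, keeping the Section 10.1 condition of no other biologic in the gap, who have a pre-interruption evaluation at or after 12 weeks from enrollment and who restart Humira. Section 10.1 does not say what kind of data after the gap is needed, so state that dosing or safety data suffice; otherwise early stoppers could be removed at that step instead.
- Report the number restarted, the number evaluated at or after 12 weeks from restart, and the number without that evaluation by recorded reason: lack of effect, adverse event, end of follow-up, not assessed.
- Show stops for lack of effect or an adverse event as unsuccessful re-treatment, beside the score summaries.
- Keep the two-timepoint paired summary as supportive.

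Separately, reconcile Sections 6.0 and 6.3.2 on whether effectiveness is collected while Humira is interrupted.

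The cost is a few lines of text and one more table. Start and stop dates, interruptions and their reasons are already collected (Section 6.4.8), as is the reason for permanent discontinuation (Section 7.4). The re-treatment result is likely to look less favourable.

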10.5 Safety Analyses

For the Registry Safety Population, treatment-emergent SAEs and adverse events of interest will be summarized. Treatment-emergent SAEs and adverse events of interest are defined as: (1) new events that begin either on or after the first dose of Humira through the last dose of Humira plus 70 days; or (2) increase in severity of ongoing SAEs that had occurred before the first dose date of Humira. The number and percent of patients experiencing SAEs and adverse events of interest will be tabulated by body system and Medical Dictionary for Drug Regulatory Activities (MedDRA[®]) preferred term. The percent of patients will be presented with 95% confidence intervals. In addition, summary of SAEs and adverse events of interest by severity and relationship to registry drug will be presented.

The event rate of SAEs and of each adverse event of interest per 100 patient year of observation will be presented. Event rates will be presented with 95% confidence intervals. For patients enrolled from a prior CD study, the total number of SAEs and adverse events of interest will include the events reported during their participation in the previous study plus any events reports during the Registry.

In addition, Observational AEs: SAEs and AEs of interest occurring from the first dose of Humira in the registry through the last contact including re-enrollment period and during the HCP process will be tabulated.

For the 'Episodic Dosing' Population, following analyses will be provided:

- Summary of SAEs and AEs of special interest will be provided for patients with episodic dosing and without episodic dosing.

- Summary of SAEs and AEs of special interest will be provided before the treatment interruption and after the treatment interruption for patients with episodic dosing.
- For each SAE and AE of special interest, and each episodic dosing, a shift table to summarize number and percentage of patients who have the event or not before the treatment interruption and after the treatment interruption.

For the Re-enrollment Safety Population, the number and percent of patients experiencing SAEs and AEs of interest during the re-enrollment period will be tabulated by body system and MedDRA preferred term. In addition, the number and percent of patients experiencing SAEs and AEs of interest collected between registry discontinuation and re-enrollment based on a retrospective review of their patient records will be tabulated separately.

For HCP Safety Population, the number and percent of patients experiencing SAEs and AEs of interest collected on HCP questionnaire during the HCP process will be tabulated by body system and MedDRA preferred term.

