6.3.1 Safety Variables

The physician will be asked to document serious adverse events and adverse events of interest on eCRFs (Section 7.5).

Serious adverse events and adverse events of interest as defined in Section 7.1.1 and Section 7.1.2 respectively, will be reported to AbbVie from the time the physician obtains the subject's authorization to use and disclose information (or the subject's informed consent) throughout the patient's participation in the Registry, up to 6 years. In the event adalimumab therapy is interrupted, SAEs and adverse events of interest will be collected throughout the interruption. If treatment with adalimumab is permanently discontinued for any reason, patients should be encouraged to continue in the registry or the direct to HCP process for a full 6 year observation period irrespective of future treatment decisions so important safety information can be obtained, as outlined in Section 6.0.

SAE reports will be completed and submitted using an electronic version of AbbVie's standard SAE form (Section 7.5).

Additional information on the adverse events of interest will be collected on separate data collection forms. These forms will capture specific information relevant to the event of interest.

In case of pregnancy, AbbVie must be notified within 1 working day of a site's learning if a female subject becomes pregnant during the registry. No clinical data on the use of adalimumab in pregnant women is available. For details please refer to the product prescribing information. Information regarding the outcome of any pregnancy occurring in a registry patient will be collected (Section 7.6). Patients who become pregnant and interrupt their Humira (adalimumab) therapy may remain in the Registry.

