7.6 Pregnancy

Pregnancy in a registry patient must be reported to AbbVie within 1 working day of the site becoming aware of the pregnancy. Pregnancies will be collected from the date of the first dose through 150 days following the last dose of registry dose.

Physicians should refer to their local prescribing information when making treatment decisions for patients who become pregnant while being treated with Humira in the Registry. Patients who become pregnant and interrupt their Humira therapy should

remain in the registry and should continue to be monitored for new SAEs and adverse events of Interest.

All female patients who become pregnant while enrolled in the registry will be followed from the time of pregnancy is reported until the outcome of the pregnancy is known. Information regarding a pregnancy occurrence in a registry patient and the outcome of the pregnancy will be collected.

Pregnancy in a registry patient is not considered an adverse event. However, the medical outcome of an elective or spontaneous abortion, stillbirth, or congenital anomaly is considered a serious adverse event and must be reported to AbbVie within 24 hours of the site becoming aware of the event.

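### The 70-day treatment-emergent rule in Section 10.5 does not fit the pregnancy outcomes that Section 7.6 collects as SAEs: after a final dose early in pregnancy or before conception, stillbirths and anomalies found at birth fall outside the treatment-emergent tables

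*Protocol*

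**What the plan says.** Section 10.5 (Safety Analyses) counts as treatment-emergent "new events that begin either on or after the first dose of Humira through the last dose of Humira plus 70 days", or a worsening of SAEs already present before the first dose. The paragraph with this definition promises percentages with 95% confidence intervals and summaries by severity and relationship. Pregnancy outcomes are not treated separately.

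Section 7.6 (Pregnancy) uses a longer period: "Pregnancies will be collected from the date of the first dose through 150 days following the last dose of registry dose". It follows women who become pregnant while enrolled "until the outcome of the pregnancy is known", and states that "the medical outcome of an elective or spontaneous abortion, stillbirth, or congenital anomaly is considered a serious adverse event". Section 7.1.3 defines a congenital anomaly as one found at or after birth, or one that causes fetal loss.

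Section 10.5 also has a second tabulation, the Observational AEs: "SAEs and AEs of interest occurring from the first dose of Humira in the registry through the last contact including re-enrollment period" and the HCP process. No 70-day limit applies there. A rate is promised as well: "The event rate of SAEs and of each adverse event of interest per 100 patient year of observation will be presented", with 95% confidence intervals. The text does not say whether its numerator is restricted to treatment-emergent events.

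On which pregnancies are reported, Section 6.3.1 says "AbbVie must be notified within 1 working day of a site's learning if a female subject becomes pregnant during the registry".

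**The concern.** A pregnancy outcome can occur many months after the exposure that matters. A rule based on the date of the event, counted from the last dose, suits an infection or an allergic reaction. It suits a stillbirth or an anomaly poorly, because the relevant exposure lies at conception or in early pregnancy. Section 7.6 recognises this by collecting pregnancies well past 70 days, but Section 10.5 then applies the 70-day rule to their outcomes.

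The tables with the fuller analysis would therefore omit some outcomes of exposed pregnancies, and they would do so according to when treatment stopped and whether it resumed. Section 6.3.1 states that no clinical data on use in pregnant women are available, so the few outcomes that this registry records deserve a denominator that fits them.

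Intake is a second weakness. Sections 7.0 and 7.4 say that SAEs are recorded through the HCP process. The content described for that process (Table 1 footnote, Section 7.8) and for the re-enrollment gap review (Section 7.7) is hospitalizations, surgeries, adverse events of interest, and medications for Crohn's disease. The list of adverse events of interest in Section 7.1.2 names no pregnancy outcome.

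**Working it through.** The protocol gives no figure of its own on this point, so the check is date arithmetic.

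**Inputs from the protocol:** treatment-emergent window of 70 days after the last dose (10.5); pregnancy collection window of 150 days after the last dose (7.6).

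**Assumptions, not in the protocol:** term at 280 days from the last menstrual period (range 259 to 294); conception at day 14, so term is 280 − 14 = 266 days from conception; stillbirth counted from week 20 (range 20 to 28); an anomaly found at birth is dated at birth; Humira is not restarted unless stated.

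**1. Last dose during pregnancy, at gestational week g.** The window closes at week g + 70/7 = g + 10.
- Term at week 280/7 = 40 is outside when g + 10 < 40, that is, when g < 30. For term at 259 days the limit is (259 − 70)/7 = week 27; at 294 days it is (294 − 70)/7 = week 32.
- Every stillbirth is outside when g < 20 − 10 = 10. With a threshold of week 28, the limit is 28 − 10 = week 18.
- Illustration with the last dose at week 5 to 8: the window closes at week 15 to 18. A week-20 stillbirth falls (20 − 8) × 7 = 84 to (20 − 5) × 7 = 105 days after the last dose. A term birth falls (40 − 8) × 7 = 224 to (40 − 5) × 7 = 245 days after it.
- A loss before the window closes (week 15 to 18 in this illustration) is inside.

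**2. Conception c days after the last dose.** A 20-week loss falls at c + (140 − 14) = c + 126 days, and term at c + 266 days.

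| c (days) | 20-week loss | Term | Within 70 days? |
|---|---|---|---|
| 0 | 126 | 266 | neither |
| 70 | 196 | 336 | neither |
| 71 | 197 | 337 | neither |
| 150 | 276 | 416 | neither |

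For conceptions up to day 70, only an early loss could still be inside. For conceptions on days 71 to 150 the window closes before the pregnancy begins, so no outcome can qualify. Those are 150 − 70 = 80 of the 150 post-dose days, or 80/150 = 53%. This is a share of days, not of pregnancies.

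**3. Restart.** Take two women with a dose at week 6 and a stillbirth at week 30. If neither is dosed again, the window closes at week 16 and neither event counts. If one restarts after the loss, her last dose moves past the event and the same outcome becomes treatment-emergent. The classification then depends on treatment given after the outcome.

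**4. Where the excluded events go.** They enter the Observational AE tabulation, or the re-enrollment and HCP tabulations, if they are reported. Section 10.5 says only that observational events will be tabulated; it states no confidence interval and no split by severity or relationship. Nothing separates a pregnancy exposed in its first weeks from one in a woman long off Humira.

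**5. Sections 6.3.1 and 7.6.** A woman still enrolled who becomes pregnant more than 150 days after her last dose is reportable under 6.3.1 but lies outside the 7.6 window. The 7.6 follow-up sentence nevertheless covers all who become pregnant while enrolled. A woman who leaves the registry and conceives within 150 days is inside the 7.6 window but is not covered by the 6.3.1 wording.

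**The case against.** The strongest reply is that nothing is lost. The clock starts at the last dose, so a woman who continues or restarts keeps her outcome inside the window. The observational tabulation runs to last contact without a cut-off, and the rate per 100 patient-years is not expressly limited to treatment-emergent events. A collection period and a classification window also serve different purposes, so 70 and 150 days are not in themselves contradictory. The onset date of an anomaly is a convention that an analysis plan could settle.

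Much of this stands. A reader might infer that most exposed pregnancies drop out, or that the main tables would show few or no such events whatever the true risk. The protocol does not support either statement: it gives no share of pregnant patients who stop, continue or restart, and the observational tabulation exists. Different window lengths alone would not be an error either.

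The misclassification remains. Even with a favourable dating convention for anomalies, a stillbirth at or after week 20 is outside when the final dose precedes week 10. The observational tabulation cannot stand in for an analysis by exposure, since it does not separate exposed from later pregnancies. Nor is this merely detail left to the analysis plan, because the protocol itself fixes the definition without exception.

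A fair objection to one possible remedy also stands. Calling outcomes up to about day 416 treatment-emergent would place them outside the on-treatment plus 70-day risk time used for other SAEs. A separate table avoids this.

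**Conclusion.** The point holds in a limited form. Without a restart, stillbirths and anomalies detected at birth cannot be treatment-emergent when the last dose precedes conception or falls early enough in pregnancy. That limit is about week 30 for term births and week 10 for all stillbirths counted from week 20. Conceptions on days 71 to 150 can never yield a treatment-emergent outcome, and a later restart changes the status of an identical event.

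These results rest on the assumed gestation lengths and, for anomalies, on dating the event at birth. The number of pregnancies affected is unknown and cannot be derived from the protocol. The consequence is a poorly fitting classification and a weak denominator, with a gap in the described HCP and re-enrollment gap data. It is not a loss of reported SAEs. It is worth correcting because the correction is small.

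**What to change.** - **Section 10.5:** keep the 70-day rule for all other SAEs. Summarise abortion, stillbirth and congenital anomaly in a separate table by exposure. Count a pregnancy as exposed if its conception or any part of it falls between the first dose and 150 days after the last dose. Take the last dose as the most recent one before the outcome, so that a later restart does not alter the class. Report per exposed pregnancy with 95% confidence intervals, and show pregnancies conceived later separately.
- **Sections 6.3.1 and 7.6:** reconcile the wording on which pregnancies are reported and followed.
- **HCP questionnaire and re-enrollment gap form (Table 1 footnote, 7.7, 7.8):** add pregnancy and its outcome, in line with the SAE collection stated in 7.0 and 7.4.

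The cost is one extra table, a few sentences and one item on two forms. Dosing dates are already collected; a conception or gestational date is needed for each pregnancy.
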